8.3.2 Scoring the C-SSRS

The C-SSRS lifetime-recent screener score is determined based on the highest question number (1-6B) to which a participant responds “yes”. For example, a score of 5 would be assigned to a participant who responded “yes” to Question 5 and any or all preceding questions. Please consult *Appendix B* of this protocol for additional C-SSRS scoring criteria.

The additional items related to suicide attempts and lethal means will not be included in the C-SSRS score but will be compared across intervention groups.

8.3.3 Risk Factors for Suicide (INQ)

Reduced risk factors for suicide including perceived burdensomeness and thwarted belongingness will be measured at baseline and six months utilizing the Interpersonal Needs Questionnaire (INQ).¹⁴ The INQ was developed from the Interpersonal Theory of Suicide to measure both perceived burdensomeness and thwarted belongingness which are proximal causes of desire for suicide.¹⁵ The INQ underwent refinement in 2012 and was reduced from 25 to 15 items.¹⁵ Respondents indicate of 15 questions how true each is for them on a scale of 1 to 7, with 1 being “not true at all for me” and 7 being “very true for me.”

The 15 items are valid and psychometrically sound for measuring perceived burdensomeness and thwarted belongingness in young and older adults.^{15,105} A study in 2014 evaluated factor structure, internal consistency, and concurrent predictive validity of the INQ versions with adolescent psychiatric inpatients and found the 15 item version to have acceptable internal consistency.¹⁰⁶

8.3.4 Stress

Stress level will be assessed for participants measured as a change in score from baseline at 6 months using the NIH Toolbox Stress and Self-Efficacy Scales Perceived Stress measure. This measure comes from the Emotion Battery of the NIH Toolbox and was selected because it is validated and psychometrically sound to measure individual perceptions about the nature of events and their relationship to the values and coping resources of an individual.² The measure is comprised of ten items which are scored and granted a t-score specific to adult or adolescent participants.⁹⁹

8.3.5 Alcohol and Illicit Drug Use

Alcohol and illicit-drug use will be measured at baseline and 6 months with questions adapted from the Youth Risk Behavior Survey.¹⁰⁷ Additional questions will be included to measure self-reported changes in alcohol or illicit-drug use since the beginning of the COVID-19 pandemic.

8.3.6 Depression

Presence of depressive symptoms, depression, and depression severity will be screened for at baseline and 6 months as an indicator of mental distress. The Patient Health Questionnaire-9 (PHQ-9) is a widely used tool to screen for depression in primary care and other non-psychiatric settings.^{17,19,108} The tool is composed of 9 questions each with a response of 0-3 which generate a score from 0-27 with higher scores indicating a greater degree of depression.¹⁹ Scores are categorized in the following manner: a score of 5-9 is considered minimal depression, 10-14 is considered mild major, 15-19 is moderate major, and ≥ 20 is severe major.¹⁹ The PHQ-9 has been shown to be a valid and reliable measure of depression severity in adult and adolescent populations; this study will utilize PHQ-9 adult and PHQ-A adolescent versions for the corresponding age groups.^{17-19,108,109}

8.3.7 Anxiety

Anxiety will serve as an indicator of mental distress and will be screened for at baseline and six months. Symptoms of anxiety will be assessed using the GAD-7, a brief self-report scale frequently used in the identification of Generalized Anxiety Disorder. The GAD-7 was validated in 2006 as a valid and psychometrically sound measure with good sensitivity (89%) and specificity (82%).²⁰ The tool is similar to the PHQ-9 in its structure and scoring with seven items and possible scores of 0-21. Higher scores indicate a greater severity of generalized anxiety symptoms²⁰. Since the original validation, the tool has been confirmed as valid for detecting anxiety in both adult and adolescent populations.^{21,110,111}

8.3.9 Uptake of Outpatient Mental Health Services

Current engagement and any engagement since study enrollment in outpatient mental health services will be measured as dichotomous variables (yes/no) at 6 months through self-report.

9. Description of Interventions

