8.3 Secondary Outcomes & Assessment

Secondary outcomes include suicide ideation (C-SSRS) self-harm and suicidal behavior; presence of risk factors for suicide including those theoretically related: perceived burdensomeness, and thwarted belongingness (INQ); background risk factors including stress (NIH Toolbox), alcohol and illicit drug use, depression (PHQ-9); and anxiety (GAD-7); and attendance at mental healthcare appointments.

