12.1 Data Collection

All data for this study will be collected via online REDCap surveys. *Table 2* includes a list of all study variables, which aim they are associated with, and which tool will be used for assessment.

Table 2: MHAPPS Trial Variables & Other Data Elements

Variables			
Outcomes	Tool	Survey Collected	Source
Loneliness	NIH Toolbox – Social Relationship Scales - Loneliness Scale	Aim 1 Survey; Aim 2 Outcome Survey	REDCap
Suicidal ideation & behavior	C-SSRS Screener	Aim 1 Survey; Aim 2 Outcome Survey	REDCap
Recent suicide attempts, suicide completion, & self-harm; lethal means	6-Months Suicide Attempts Survey	Aim 1 Survey; Aim 2 Outcome Survey	REDCap
Perceived Burdenomeness; Thwarted Belongingness	INQ-15	Aim 1 Survey; Aim 2 Outcome Survey	REDCap
Stress	NIH Toolbox – Perceived Stress 10	Aim 1 Survey; Aim 2 Outcome Survey	REDCap
Alcohol and Illicit drug use	Youth Risk Behavior Survey Questions	Aim 2 Baseline Survey; Aim 2 Outcome survey	REDCap
Depression	PHQ-9	Aim 1 Survey; Aim 2 Outcome Survey	REDCap
Anxiety	GAD-7	Aim 1 Survey; Aim 2 Outcome Survey	REDCap
Uptake of outpatient mental health treatment	N/A	Aim 2 Baseline Survey; Aim 2 Outcome Survey	REDCap
Exposure Variables		Survey Collected	Source
Date of birth, age in years, age category (adult/peds)		Aim 1 Survey	REDCap

MHAPPS Trial Protocol

SLHS Applied Research

December 30,2020

Sex at birth	Aim 1 Survey	REDCap
Race and ethnicity	Aim 1 Survey	REDCap
Zip code of residence (urban/rural)	Aim 1 Survey	REDCap
Gender identity & sexuality	Aim 2 Baseline Survey	REDCap
Religion	Aim 2 Baseline Survey	REDCap
Variables related to employment and occupation of self/parent	Aim 1 Survey	REDCap
Education / maternal education	Aim 1 Survey	REDCap
Living situation (permanent, temporary)	Aim 1 Survey	REDCap
Number of people at home	Aim 1 Survey	REDCap
Caregiving for dependent(s)	Aim 1 Survey	REDCap
Financial security and food security	Aim 1 Survey; Aim 2 Baseline Survey	REDCap
Food access and eating habits and COVID-19	Aim 2 Baseline Survey	REDCap
Physical activity and COVID-19	Aim 2 Baseline Survey	REDCap
Perceived risk for COVID-19 & other COVID-19-related questions	Aim 1 Survey; Aim 2 Outcome Survey	REDCap
Masking practices & beliefs	Aim 1 Survey; Aim 2 Outcome Survey	REDCap
Social distancing practices & beliefs	Aim 1 Survey; Aim 2 Outcome Survey	REDCap
School attendance, extracurricular activities	Aim 2 Baseline Survey (Youth)	REDCap

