Access to healthcare and mental healthcare services	Aim 2 Baseline Survey; Aim 2 Outcome Survey	REDCap
Domestic violence	Aim 2 Baseline Survey	REDCap
Local COVID-19 prevalence	CDC or Idaho Department of Health & Welfare Prevalence Data	
Process Variables		
Aim 1 proportion of eligible participants completing survey	REDCap	
Aim 2 proportion of eligible participants enrolled	REDCap	

MHAPPS Trial Protocol
SLHS Applied Research
December 30,2020

Participant feedback on phone call (CC+ arm only)	Aim 2 Outcome Survey	REDCap	
Participant feedback on content and timing of caring messages; satisfaction with caring contacts	Aim 2 Outcome Survey	REDCap	
Rating of quality of "connectedness" with participant		Mosio and/or REDCap	
"Dose" of follow-up contact: timing, type (phone vs text), and number of attempted and successful contacts from the Hotline		Mosio and/or REDCap	
"Dose" of Caring Contact text messages: date/time of each text message sent (* 11 text messages)		Mosio and/or REDCap	
Other Variables	Tool	Aim Collected	Source
Does cell phone on record belong exclusively to study participant or is it shared?		Aim 2 Baseline Survey	REDCap
Cell phone number, email address, contract preferences, mailing address, and alternative modes of contact		Informed Consent Form, Aim 1 Survey; Aim 2 Baseline Survey	REDCap
Eligibility and willingness to be contacted about Aim 2 participation		Aim 1 Survey	REDCap
Death		CDC or Idaho State Vital Records	

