6.3 Exploratory endpoints

- Suicide attempts and lethal means will be summarized and compared across treatment arms. Questions will include the number of attempts and aborted attempts and lethal means.
- Psychological stress will be measured using the NIH Toolbox and assessed as change from baseline. This instrument results in a continuous T-score outcome.
- Changes in alcohol and illicit drug use will be described. Participants will be asked if they are current, ever, or never user of a variety of substances (tobacco, alcohol, marijuana, other illicit drugs), as well as the amount and frequency of use for current users. Participants will be asked about whether or not the amount they use has changed. Changes from baseline to 6 months in the current/ever/never question will be summarized for each substance, as well as reporting the number and percentage of participants with any increase or any decrease.
- The GAD-7 scale will be used to measure anxiety. Participants respond to seven items and receive possible scores of 0-21.
- Attendance at mental healthcare appointments will be measured as a dichotomous variable (yes/no) at 6 months through self-report.

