7.2.1 Primary analysis

The effects of the intervention will be modeled separately in patients and providers/staff. **Linear regression with robust standard errors will be used to determine whether the primary outcome differs between CC+ vs CC**, adjusting for the baseline score as a precision variable. Multiple imputation will be used to account for missing data (see 7.3).

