7.2.2 Secondary analyses

All outcomes will be modeled separately in the patient and provider/staff populations. Linear regression will be used to estimate the difference in means for continuous outcomes; for binary outcomes, GLM models with an identity link will allow for the estimation of the difference in proportions. Robust/sandwich standard errors will be used to allow for departures of the observed standard errors from classic model assumptions.

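### Mental health service use: continued pre-enrolment care counts as a yes and no analysis uses the baseline answer, so an effect on new uptake cannot be separated from continuation

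*Protocol*

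**What the plan says.** **Name.** The endpoint has two labels. The heading of Protocol 8.3.9, the row in Protocol Table 2 ("Uptake of outpatient mental health treatment") and the matching row in SAP Table 1 speak of uptake. The protocol synopsis, Protocol 8.3 ("and attendance at mental healthcare appointments") and SAP 6.3 speak of attendance.

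**Definition.** Protocol 8.3.9 defines two items: "Current engagement and any engagement since study enrollment in outpatient mental health services will be measured as dichotomous variables (yes/no) at 6 months". SAP 6.3 has one: "Attendance at mental healthcare appointments will be measured as a dichotomous variable (yes/no) at 6 months through self-report". The SAP does not say which protocol item this is, and gives no look-back period.

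**Who can enter.** The Aim 2 criteria (Protocol 5.1.2, SAP 5.2) turn on distress scores and phone access. Being in mental health care already is not an exclusion.

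**Baseline.** Protocol Table 2 schedules the uptake row for both the Aim 2 Baseline Survey and the Aim 2 Outcome Survey. A related row, "Access to healthcare and mental healthcare services", is also scheduled for both.

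**Analysis.** SAP 7.2.2 says that "for binary outcomes, GLM models with an identity link will allow for the estimation of the difference in proportions", with no baseline term. Baseline adjustment is stated only for the primary outcome, in SAP 7.2.1: "adjusting for the baseline score as a precision variable". Baseline care is not named among the effect modifiers in SAP 6.5 (its open-ended last clause could admit it), the subgroups in SAP 7.2.3 or the imputation cells in SAP 7.3.

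**Tier.** The endpoint is secondary in Protocol 8.3 and exploratory in SAP 6.3.

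**The concern.** The arms differ only by the introductory call, and Protocol 9.1 includes helpful resources among its usual topics. Starting outpatient care is therefore a plausible effect of CC+, and a reader who sees a result labelled *uptake* will take it to mean that.

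The definition does not isolate that event. Take three participants:

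- A was in therapy before enrolment and is still attending at 6 months: yes on both protocol items.
- B was not in care and started after the call: yes on engagement since enrolment, and yes on current engagement if still attending.
- C was in care at enrolment, attended once more and stopped: yes on engagement since enrolment, no on current engagement.

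Only B is new uptake, yet A and B can look the same at 6 months. Only the baseline answer separates them, and no stated analysis uses it. C has a clear value on each protocol item but none on the single SAP item until the SAP says which item it means. What is at stake is how this endpoint is read, and how precise it is.

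**Working it through.** **Figures in the plan.** Neither document gives a rate, effect size or power for this endpoint. The only power statement (Protocol 13.2, SAP 5) concerns loneliness: 165 per arm per stratum, 5 units, 80% power, 70% retention. It states no SD, so it cannot be reproduced. Solved backwards with 165 × 0.70 = 115.5 per arm it implies an SD of about 13.6. Nothing below depends on that.

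**Inputs from the plan.** About 115 completers per arm per stratum (70% of 165); two-sided alpha 0.05 (Protocol 13.1); difference in proportions as the effect measure (SAP 7.2.2).

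**Inputs assumed, because the documents give none.** Share already in care π = 10%, 30% or 50%. New uptake among the rest 12% (CC) and 25% (CC+). Continuation among those in care r = 95% in both arms.

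**Algebra.** The proportion answering yes in an arm is p = π·r + (1 − π)·p_new. With equal r in both arms the first term cancels, so the observed difference is (1 − π)(0.25 − 0.12).

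**At π = 30%.**

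- CC: 0.30 × 0.95 + 0.70 × 0.12 = 0.369
- CC+: 0.30 × 0.95 + 0.70 × 0.25 = 0.460
- Difference: 0.091, which is 0.70 × 0.13

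**Power at π = 30%**, as Φ(difference/SE − 1.96):

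- As written: SE = √[(0.369 × 0.631 + 0.460 × 0.540)/115] = 0.0647; 0.091/0.0647 = 1.41; power about 29%.
- Only those not in care (n = 0.70 × 115 = 80.5 per arm): SE = √[(0.12 × 0.88 + 0.25 × 0.75)/80.5] = 0.0603; 0.13/0.0603 = 2.15; power about 58%.
- All participants, stratified by baseline care: SE = √[(0.30 × 2 × 0.95 × 0.05 + 0.70 × 0.2931)/115] = 0.0451, where 0.2931 = 0.12 × 0.88 + 0.25 × 0.75; 0.091/0.0451 = 2.02; power about 52%.

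The same formulas give the other rows:

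| Share in care | Difference as written | Power as written | Power, all participants, stratified | Difference, not in care | Power, not in care |
|---|---|---|---|---|---|
| 10% | 11.7 points | 53% | 67% | 13 points | 69% |
| 30% | 9.1 points | 29% | 52% | 13 points | 58% |
| 50% | 6.5 points | 17% | 35% | 13 points | 44% |

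**How much of the yes group is existing care (CC arm).** At 30%: 0.285/0.369 = 77%. At 10%: 0.095/0.203 = 47%.

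**Relaxing equal continuation.** Keep π = 30% and the same new uptake, but let continuation be 75% in CC and 88% in CC+:

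- CC: 0.30 × 0.75 + 0.70 × 0.12 = 0.309
- CC+: 0.30 × 0.88 + 0.70 × 0.25 = 0.439
- Difference: 0.130, so there is no shrinkage, and power is about 54%

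**The case against.** The strongest reply is that the endpoint is attendance and *uptake* is only a heading and a table label. The protocol's outcome lists and SAP 6.3 say attendance, and for attendance a person who keeps going to existing therapy is correctly a yes. This stands. The documents show a label that does not match its definition, and two possible questions under one variable. They do not show a scoring error.

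A reader might infer that any CC+ effect on this endpoint is diluted. The documents do not support that. The shrinkage applies to an effect on new entry into care and needs similar continuation in both arms; the call could also help people stay in care, and the last calculation then shows none. Nor are prior users counted because of their past: they count only if they engage after enrolment.

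A reader might also infer that the arm comparison is biased, or that most yes answers would be old care. Randomization should balance prior care between arms, so bias does not follow. The share of yes answers that is old care depends entirely on an assumed figure.

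Finally, limiting the analysis to people not in care would drop part of the randomised sample and discard any effect on continuation. SAP 5.3 evaluates primary and secondary endpoints in the ITT population. That stands against restriction as a replacement. It does not stand against using the baseline answer as an adjustment.

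**Conclusion.** The point holds as a cheap improvement to a low-tier endpoint. Under both definitions continuing care is a yes, existing care is no bar to entry, and no stated analysis uses the scheduled baseline answer. An effect on new uptake is therefore attenuated by (1 − share already in care) on the planned difference scale, provided continuation is similar in both arms.

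The true size is unknown. Under the stated assumptions, a 13-point effect among people not in care appears as 11.7, 9.1 or 6.5 points. Even with adjustment or restriction, power at 30% to 50% in care stays between 35% and 58%, so a null result would still be inconclusive. The loneliness analysis and its conclusion are unaffected.

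**What to change.** In SAP 6.3 and 7.2.2:

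1. State which protocol item is analysed: current engagement, any engagement since enrolment, or each separately.
2. Keep the all-participant comparison, adjusted for or stratified by care status from the Aim 2 Baseline Survey.
3. Report the arm difference separately for those not in care at baseline (new uptake) and those already in care (continuation).
4. Use one label, *uptake* or *attendance*, in both documents, and reconcile the secondary and exploratory status.

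Before relying on this, confirm that the baseline item is on the form. Table 2 lists it, but the short description of the baseline survey in Protocol 6 does not mention it. The item should ask about care before enrolment, because the survey goes out as a link and the plan does not say that it is completed before assignment.

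The cost is SAP wording and slightly more analysis. If Table 2 is correct, no new data are needed. The new-uptake estimate will rest on a smaller subset defined at baseline and should be presented as such.

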9.1 Caring Contacts with Introductory Call (CC+)

Caring Contacts will consist of one introductory phone or video conversation to establish a connection between the study participant and the follow-up specialist. The introductory phone call will be unscripted, but will generally include the following elements: an introduction, if appropriate (based on participants' survey scores) a safety/wellbeing check, a review and discussion of the elements of mental distress on which the participant scored highest, a discussion of any relevant resources that may be helpful to the participant, and a description of what to expect with the caring text messages that will

follow. Hotline follow-up specialists will attempt to complete the phone call over a two-week period following study enrollment. If the phone call cannot be completed in two weeks, the Hotline will initiate the text message portion of the intervention.

The call will be followed by a series of 11 personalized caring contacts sent over the course of 6 months via text message or email.¹¹² The frequency and cadence of caring text messages will be consistent for all participants and was determined following consultation with PLES Advisors to ensure it is culturally and age appropriate. Caring text messages will be sent using a HIPAA-compliant program called Mosio according to the following schedule: weeks 1, 2, 3, 4, 6, 8, 10, 12, 16, 20, and 24. While there is no expectation that participants respond to the text messages, some participants may choose to respond. Hotline Follow-Up Specialists will review incoming text messages and phone calls from study participants and will respond according to the Hotline's internal operating procedures. These additional contacts will take place outside of the structured study protocol and will not be under the purview of SLHS institutional policies. Mosio will track the number and content of individual responses to study text messages, and this information will be shared with the study team. Response and ongoing contacts as part of the Hotline's processes will not alter the timing or frequency of caring contacts established by the study protocol. Data collected and stored in Mosio will become part of the study dataset and may be analyzed as part of process evaluation or other analyses.

9.2 Caring Contacts without an Introductory Call (CC)

Participants will be sent caring text messages according to the schedule above. No introductory phone or video call from the Hotline will be made.

9.3 Definition of Full Intervention

Participants must be sent at all 11 caring text messages (all participants), and complete a phone call (if randomized to CC+) to be included in the Per Protocol analysis group.

9.4 Process Evaluation

The study will include a process evaluation to assess uptake of surveys and delivery of the interventions, with process data collected and evaluated throughout the enrollment period. Specifically, the study will measure the proportion of invited survey participants who complete surveys for Aim 1. For Aim 2, the proportion of eligible participants who enroll in the clinical trial will be measured. The proportion of Aim 2 participants in the CC+ arm who are successfully contacted with an introductory phone call within two weeks of enrollment will also be measured, along with the proportion of participants in each study arm who complete the full intervention. The "dose" of each intervention received (phone call, number

of text messages sent) will be recorded and assessed. Data will also be collected and reviewed to assess how well participants like the Caring Contacts messages received as part of this trial.

10. Discontinuation and Participant Withdrawal

10.1 Participant Discontinuation and Withdrawal from the Study

Participants are free to withdraw from participation in the study at any time upon written request to the MHAPPS email account ([contact]). Additionally, study investigators may discontinue a participant from the study for the following reasons, but not limited to:

1. Lost to follow-up; unable to contact subject (see section *10.2 Lost to Follow-Up*)
2. Any event or medical condition or situation occurs such that continued collection of follow-up study data would not be in the best interest of the participant
3. Any event or situation occurs in which the safety or wellbeing of study staff is compromised by allowing a participant to continue to participate in the research
4. The participant meets an exclusion criterion or fails to meet an inclusion criterion (either newly developed or not previously recognized) that precludes further study participation

The date of discontinuation and reason for discontinuation or withdrawal from the study will be recorded in the MHAPPS Trial study records.

